Randomization Procedure: Randomization will be performed using a computer-generated randomized allocation sequence made available online for the clinic care coordinator, and will be stratified by WeeFIM score as mild (18-54), moderate (55-90) and severe (\geq 91) disability, and age group (1-11 and 12-18 years), and performed using random permuted blocks to ensure assignment of subjects to the intervention and usual care groups is balanced over time. Participants randomized to MyChild^{CMC} will receive support to install the app, a temporary password (modified upon login) and full MyChild^{CMC} access. At the first login (in the clinic), the care coordinator will guide participants through baseline surveys and first assessment of crosscutting symptoms/ caregiver burden, thereafter caregivers will use the MyChild^{CMC} app over 3 months. All alerts about changing patient health status/caregiver burden will be directed to the care coordinator, who will follow-up with families to determine if an action, or a visit with a HCP or social worker is needed. The care coordinator will also access the dashboard to see participants not adherent with MyChild^{CMC} use and follow-up with those in need of supports. Participants randomized to usual care will receive general self-management education, be encouraged to monitor their child's symptoms/caregiver burden and identify deteriorations but without MyChild^{CMC}, and will complete surveys and provided incentive on the same schedule as the intervention group.

Data Collection: Upon first login, caregivers will complete a demographic survey (only once), including caregiver education level, a series of baseline surveys assessing the child (QOL) and caregiver (satisfaction, self-management skills, QOL and burden). Also, we will collect caregiver health literacy (only once) to be used in analysis of spec aims 3, and severity of child disability using WeeFIM which will be used in analysis of aims 2 and 3. 2 Baseline and follow-up surveys will be collected online by RedCAP within 3 months.

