Data Analysis: The primary outcome is the CPCHILD total score, which will summarize the child's QOL at baseline, and at 3, 6, 9 and 12 months of follow-up. Secondary outcomes include additional CPCHILD sub-domains beyond the total CPCHILD (comfort and emotions; communication and social interaction; health; and overall QOL), child ED/hospital admission, and caregiver satisfaction, self-management skills, caregiver burden, and HCP satisfaction. The primary and secondary analyses will be performed in accordance with intention-to-treat, with patients analyzed in accordance with the randomized treatment assignment irrespective of compliance. Numeric outcome variables exhibiting positive skewness may be transformed to better approximate normality. Analyses will be performed with SAS version 9.4 or higher. Standard statistics including means, standard deviations, medians, and interquartile ranges for continuous variables and frequencies and percent for categorical variables will be used to compare characteristics of randomized vs. non-randomized patients and to compare baseline characteristics between randomized groups. Open-ended questions of caregiver and HCP satisfaction will be analyzed using standard qualitative analysis as described in Aim 1.

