The primary analysis of the CPCHILD total score will be performed by applying a linear mixed effects model to compare the mean QOL score over the 3, 6, 9 and 12-month assessments between the intervention and control groups. The mixed effects model will incorporate an unstructured covariance matrix to account for serial correlation within the same patients, and will include fixed effect terms for the randomized treatment assignment, the baseline CPCHILD total score, Clinic, and the WeeFIM and age group randomization strata as well as interaction terms between each of these factors and follow-up visit. Adjustment for the baseline CPCHILD total score will account for any baseline imbalances in the outcome variable and regression to the mean, thereby increasing statistical power. In addition to the primary comparison of the mean CPCHILD total score over all 4 follow-up assessments between the randomized groups, secondary contrasts will be constructed to estimate treatment effect on the mean total score at each individual follow-up visits and to compare the size of the treatment effects between different follow-up visits to determine if the treatment effect attenuates or increases over time. Secondary outcomes will be compared between the randomized groups using similar linear mixed models for numeric outcomes (e.g., other CPCHILD subscales, caregiver/HCP satisfaction, PAM score, and burden score) or generalized linear models with use of robust empirical standard errors for categorical outcomes. Similar analysis will be used to compare caregiver burden subscales (stress and coping). The rate of ED visits and hospital admissions will be compared between randomized groups using negative binomial regression, possibly augmented to account for 0-inflation if the proportion of subjects with 0 ED events or hospitalizations exceeds that accounted for by the negative binomial model

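### Months 6, 9 and 12 of Aim 2's primary CPCHILD contrast appear in no procedure or payment text, and the link between Aim 2 and the 3-month stage is never stated

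*Combined protocol and SAP*

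**What the plan says.** **Analysis (section 4, item 9, AIM 2).** The primary outcome is the CPCHILD total score "at baseline, and at 3, 6, 9 and 12 months of follow-up". The primary analysis is a linear mixed model "to compare the mean QOL score over the 3, 6, 9 and 12-month assessments between the intervention and control groups". Its fixed effects are the randomised arm, the baseline score, clinic, and "the WeeFIM and age group randomization strata as well as interaction terms between each of these factors and follow-up visit". Secondary contrasts estimate the effect at each visit and are meant "to compare the size of the treatment effects between different follow-up visits to determine if the treatment effect attenuates or increases over time".

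**Procedures (section 4, item 6).** Randomisation "will be stratified by WeeFIM score as mild (18-54), moderate (55-90) and severe" disability, "and age group (1-11 and 12-18 years), and performed using random permuted blocks". Intervention caregivers then use the "app over 3 months. All alerts about changing patient health status/caregiver burden will be directed to the care coordinator". The Data Collection paragraph says: "Baseline and follow-up surveys will be collected online by RedCAP within 3 months". It gives no visit times. The usual care arm follows the same survey schedule. The same paragraph says that the WeeFIM measurement will serve the Aim 2 and Aim 3 analyses.

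**Elsewhere.**
- The opening of item 9, under the label Preliminary Impact, places the primary QOL outcome at baseline, 1 and 3 months and defers detail to a phase 2 that is not defined.
- Section 6, item 4, pays 40 dollars for enrolment and baseline and 40 dollars for each of two follow-up surveys, 120 in total.
- Section 4, item 4, lists the stages by year and ends in year 3 with a 3-month feasibility pilot. Additional Consent Considerations, item 1, also speaks of a pilot.
- Section 4, item 3, and the hospital's study description give a study length of 5 years.

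**The concern.** The primary contrast averages four visits, and the described collection reaches only the first of them. Item 6 asks for every procedure from screening to closeout, so it is where surveys at 6, 9 and 12 months should appear.

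If the procedures govern, the primary contrast has to be replaced. The candidates (the 3-month effect, a mean of months 1 and 3, or something else) are different quantities, and none is the average over a year. Without an amendment made before outcome data are examined, the choice could be made with results in view. The question of whether the effect lasts would be lost. Aim 3 adds its moderator terms to the same model, so it would be answering about a different period too.

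**Working it through.** **Step 1. Follow-up times, source by source.**

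| Source | Follow-up of the QOL outcome |
|---|---|
| Item 9, AIM 2 | 3, 6, 9, 12 months |
| Item 9, Preliminary Impact | 1, 3 months |
| Item 6, Data Collection | within 3 months, visits not listed |
| Section 6, item 4 (payments) | two surveys, times not given |

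Baseline is common to the first three sources and is paid for in the fourth. Month 3 is named in the first two and fits the window in the third. Months 6, 9 and 12 stand only in the AIM 2 text. Payments are indirect evidence, but two surveys match months 1 and 3 and cannot cover four visits.

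**Step 2. What the Aim 2 model can estimate.** Write the mean score at visit v (v = 3, 6, 9, 12) as μ_v + δ_v × (arm) + covariate terms. Because arm is interacted with visit, each δ_v is a separate parameter.

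- Primary contrast: (δ_3 + δ_6 + δ_9 + δ_12) / 4.
- Comparison of visits: δ_v − δ_w for two different visits.

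With post-baseline data at month 3 only, the data inform δ_3 and nothing else. A contrast is estimable if adding it to the design matrix does not raise the rank. That holds for δ_3. It fails for the four-visit mean, for δ_6, δ_9 and δ_12, and for every difference between visits. With all four visits collected, all of these are estimable. The unstructured covariance matrix does not help, since its elements for uncollected visits are not estimable either. A 1-month score has no parameter in this model.

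One could equate δ_3 with the four-visit mean by assuming a constant effect. The plan makes no such assumption and sets out to test for change over time.

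**Step 3. Is the sample size affected?** Inputs from AIM 2, Statistical Power: SD 15.4, difference 6.59, two-sided α 0.05, power 85%, loss 10%. Equal allocation is assumed, as no ratio is given.

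- n per arm = 2 × (1.960 + 1.036)² × 15.4² / 6.59² ≈ 98.1, rounded up to 99.
- Total = 2 × 99 / 0.90 = 220, as the plan states.
- Power with 99 per arm: 85.3% (normal), 85.0% (noncentral t).
- With a baseline correlation of 0.5, the SD becomes 15.4 × √(1 − 0.25) = 13.3 and the detectable difference 5.71, consistent with the plan's upper limit of 5.73.

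The calculation uses one score per child and takes no credit for repeated visits, as the plan itself says. It therefore also serves a comparison at month 3 alone, if the SD and loss hold.

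**The case against.** The best defence is that two stages are described. Item 9 opens with feasibility and preliminary impact, points ahead to a phase 2, and then gives AIM 2 its own outcome, schedule, model and power. The 3-month stage is called a pilot. The study lasts 5 years and the timeline labels only three, which leaves room for a 12-month trial. The form is meant to grow by amendment. The Aim 2 model also has a clinic term that is not among the randomisation strata in item 6, and a later trial could reuse the same strata. On this reading the 1- and 3-month schedule and the 3- to 12-month schedule do not conflict.

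That reading is possible, and part of it stands: the documents do not show that 12-month follow-up was abandoned. It does not remove the problem:
- The split is stated nowhere, and the sentences about later amendments concern consents, not visits.
- Item 6 says that its own WeeFIM data serve Aims 2 and 3.
- Item 6 describes the only randomisation with the strata that the Aim 2 model uses.
- Even if Aim 2 is a later trial, its collection at 6, 9 and 12 months is undescribed. So is whether pilot dyads enter it.

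Some stronger readings are tempting but unsupported. A reader might infer that the primary contrast has no matching data at all; baseline and month 3 do match. A reader might take item 6 as the only randomisation Aim 2 could use; it is only the one described. A reader might conclude that Aim 3 cannot be run; its moderator-by-treatment terms can be fitted to whatever visits exist, though they then concern a different time-average. ED and hospital admissions come from the data warehouse and do not depend on the survey schedule.

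**Conclusion.** The point holds and should be fixed before outcome data are examined. Three of the four visits in the primary contrast have no described collection, on either reading of the staging. That the four-visit mean and the comparisons between visits cannot be estimated is conditional: it follows if the trial runs as item 6 describes. The documents do not settle which schedule is intended.

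It would be wrong to infer that the trial is underpowered, since 220 reproduces for a single assessment. Nor can a size be put on the gap between the 3-month effect and the four-visit mean, because the documents give no information on how the effect moves over time.

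**What to change.** Before outcome data are examined, reconcile section 4, items 6 and 9, and section 6, item 4, to one follow-up schedule and one prespecified primary contrast. State whether the 3-month stage is separate from Aim 2, whether its participants enter Aim 2, and which stage the 220 belongs to. Carry the same choice into Aim 3. Then take one of two routes.

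**(A) Only the 3-month schedule is run.** List the visit times in item 6, including month 1 if intended. Fit the same baseline-adjusted mixed model to the visits collected, name one primary contrast (for example the 3-month effect), and remove the 6-, 9- and 12-month contrasts. This is a text change. The price is scientific: the trial no longer addresses effects to 12 months or their persistence.

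**(B) A 12-month Aim 2 is intended.** Say so, add the 6-, 9- and 12-month surveys to the procedures and payments, and reconcile the described app-use period with the follow-up. Cost at the current 40-dollar rate, assumed unchanged, for 220 dyads:
- One cohort, two follow-up surveys becoming four: 40 + 4 × 40 = 200 against 120 now, so 80 more per dyad, or 80 × 220 = 17,600 dollars. If a month-1 survey is kept as well: 40 + 5 × 40 = 240, so 120 more per dyad, or 26,400 dollars.
- Separate cohort: 200 per dyad, or 200 × 220 = 44,000 dollars.

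Either form of (B) also needs retention work over the longer follow-up.

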Please review these previously entered fields as you fill out the new form:
Sponsor: HRSA MATERNAL & CHILD HEALTH BUREAU Contact: [name], MPH, FAAP Senior Medical Advisor/Acting Deputy Director Division of Services for Children with Special Health Needs Maternal and Child Health Bureau [contact] office [contact] mobile [contact] Grant Number: HHSH25020170038G Awardee: University of Utah, [name] Effective Date Start: 12/19/2018
a. Are you receiving award or contract management for the sponsored funds through the University of Utah Office of Sponsored Projects?
● Yes ◯ No
If yes, select the associated OSP Proposal ID/DSS through eAward to link it to the ERICA system.
You must have a fully approved Proposal ID/DSS number through eProposal which will show up in eAward after OSP has integrated the ID. To access the eAward application, use the instructions on the OSP website.
Link to a Proposal ID/DSS through eAward

7/0/	200	21
7/9/	20	Z I

IRB_00088596

3. Participants

IRB 00088596	Created: 12/9/2015 12:01 PM

PI: [name]

Submitted: 2/12/2016

Title: SELF-MANAGEMENT INTERVENTION FOR CHILDREN WITH CHRONIC MEDICAL COMPLEXITY

		3. Participants
		-
1.	Ages of Participants:	
	Less than 7 years old	(Parental permission form needed)
	7 to 17 years old	(Parental permission and assent form needed)
	18 and older	(Consent form needed)

2. Specific age range of participants (e.g., 7-12 years old, 60+, etc.): Children age 1-20 years old with complex medical conditions and their parent caregivers

3. Indicate any vulnerable participant groups (other than children) included:

Individuals with Cognitive or Decisional Impairment

If "Other", please specify:

If "None" and no children are involved, answer the following question. Has the participant selection process overprotected potential subjects who are considered vulnerable so that they are denied opportunities to participate in research? ○ Yes ● No

4. Number of participants to be included and/or enrolled in this entire study, across all study locations: 300

At Utah prior to October 2019: 300

5. Characteristics of Participants/Inclusion Criteria:

- 1. Complex Medical Conditions ages 1-20 years with their caregivers (primary person caring for the child)
- 2. been seen at Primary Children's Hospital within 365 days,
- 3. own a smartphone or a tablet computer with Internet access
- 4. English speaking.

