Validated surveys will be used to collect data, including a 37-item Caregiver Priorities and Child Health Index of Life with Disabilities (CPCHILD) Questionnaire (child QOL), 12-item Parent satisfaction questionnaire, which includes one open-ended question assessing participant's perception of burden related to MyChild^{CMC} use, 13-item Patient Activation Measure (caregiver self-management skills), 12-item Short Form health survey (caregiver QOL), and a 6-item Newest Vital Sign (NVS) for caregiver health literacy. At each QOL, we will also collect caregiving burden summary over the past month for both the intervention and control groups. All HCP caring for CMC during the study period will be surveyed at the end of the study to assess their satisfaction with care using the 6-item HCP Satisfaction Questionnaire. ED and hospital admissions will be collected using the Intermountain enterprise data warehouse (EDW),152 an integrated database linking data of 22 hospitals in Utah and Idaho. Intermountain Healthcare provides services for > 95 % of children in Utah.

7. Are all procedures for research purposes only (non-standard or non-standard of care procedures)? Yes O No

If no, list the procedures that are performed for research purposes only (non-standard or non-standard of care procedures):

8. Is there a safety monitoring plan for this study?

🔿 Yes 🌑 No

9. Provide a summary of the statistical methods, data analysis, or data interpretation planned for this study. Factors for determining the proposed sample size (e.g., power) should be stated.

Data Analysis. We will assess Feasibility, using family's participation, retention, adherence, and dropout rates. We will also assess parent responses to interactive activities such as response to reminders and alerts, to inform the future enhancement, and the appropriateness of the alerts triggered by the MyChild^{CMC} app. Preliminary Impact: The primary outcome is QOL score, obtained at baseline, 1 and 3 months. Secondary outcomes are QOL sub-domains (comfort, emotions, communication and social interaction, health, and overall QOL), ED/hospital admissions and caregiver satisfaction. Further detail will be provided during phase 2.

AIM 2

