3.	List the identifying information you plan to collect or keep a link to (e.g. names, dates, or identification numbers such as social security numbers or medical record numbers, etc). EMPI, Encounter, Admit Date, Discharge Date, Date of Birth, Age, Sex, Race, Weight, Height, PCP, Insurance Code, Composite Score, Length of Stay, Cost, Hospital/ED Readmissions
4.	Explain why the PHI to be used or disclosed is the minimum necessary to accomplish the research objectives: The PHI is a prerequisite to identifying and pulling charts for manual review, and for administrative database information retrieval. The PHI we are collecting will be used to improve our ability to provide high quality complex medical care and will provide critical information for quality improvement.
5.	Explain why the research could not practicably be conducted without the waiver of authorization. For example, complete the following sentence: "If I had to obtain authorization, the research could not be conducted because" The PHI accessed through chart review will provide Quality Improvement (QI) data as it will be given to pediatric clinical program leaders. Impacts of QI interventions on hospitalization outcomes and patient related measures targeted at reducing re-admissions have not been evaluated. By obtaining authorization, selection bias is introduced, which minimizes the generalizability of the study outcomes.
6.	Describe your plan to protect the identifiers from improper use and disclosure, and indicate where the PHI will be stored and who will have access: All investigators and project staff sign confidentiality pledges annually and receive IRB and HIPAA privacy and data security compliance training annually. All source/legacy data files regarding patient EDW data will be stored behind the Intermountain fire wall and will be accessed only by staff members working on this study.

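### ED/hospital counts: the negative binomial comparison names neither the randomisation strata nor a prior-use count, a modest and avoidable loss of precision on a secondary outcome

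*Combined protocol and SAP*

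**What the plan says.** All references are to the combined protocol and SAP.

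- **Count model** (section 4, item 9, AIM 2 Data Analysis): "The rate of ED visits and hospital admissions will be compared between randomized groups using negative binomial regression". A zero-inflated version is an option "if the proportion of subjects with 0 ED events or hospitalizations exceeds that accounted for by the negative binomial model". No stratum, prior-use count, Clinic term or offset is named.
- **CPCHILD model** (same section): the fixed effects include "the baseline CPCHILD total score, Clinic, and the WeeFIM and age group randomization strata". The stated reason for baseline adjustment is that it "will account for any baseline imbalances in the outcome variable and regression to the mean, thereby increasing statistical power".
- **Other secondary outcomes** (same section): models similar to the primary one are promised, but as linear mixed models for numeric outcomes. The examples listed do not include ED or hospital counts, which have their own sentence.
- **Randomisation** (item 6, Randomization Procedure): permuted blocks, stratified by three WeeFIM levels and two age groups. The Data Collection paragraph adds that WeeFIM will serve the Aim 2 and Aim 3 analyses, without naming a model.
- **Data source** (item 6): "ED and hospital admissions will be collected using the Intermountain enterprise data warehouse (EDW". The waiver request (item 3) lists identifiers beginning "EMPI, Encounter, Admit Date, Discharge Date, Date of Birth" and also includes ED/hospital readmissions. A consented retrospective portion is mentioned in section 1 item 8, section 4 item 4 and the Consent Process page, but what it collects is not stated.

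**The concern.** ED and hospital use is the main utilisation outcome in Aim 2.a and a benefit that the application expects. Only the CPCHILD score is powered, so nothing else in the plan protects precision on the counts.

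In children with medical complexity, past use plausibly predicts future use. Eligibility requires having "been seen at Primary Children's Hospital within 365 days", a contact that need not be an ED visit or an admission, and the application expects 20% of participants to be inpatients. Prior use is therefore likely to vary between children in ways that the WeeFIM and age strata need not capture. The plan applies the adjustment argument to CPCHILD but not to this outcome, although the strata are already recorded and the source of the outcome appears able to supply a look-back count.

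At stake are some power and, if risk differs strongly by stratum, a standard error larger than it should be. Validity is not at stake.

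**Working it through.** **1. The plan's own figure.** This covers CPCHILD only. With SD 15.4, difference 6.59, two-sided 0.05 and 85% power, n per arm = 2 × (1.960 + 1.036)² × (15.4/6.59)² = 98.06, rounded up to 99. Then 198/0.90 = 220. Power at 99 per arm is 85.3%. The figure reproduces and is not in dispute. Nothing comparable is given for the counts.

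**2. Inputs for the counts.** From the plan: 220 children and two-sided 0.05. Assumed: 1:1 allocation (no ratio is stated), 2 events a year, dispersion k = 1 and rate ratio 0.70. All 110 per arm are counted, because warehouse counts do not need a returned survey. Stability is the share of children whose risk is the same before and after randomisation.

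**3. Unadjusted precision.** Var(log rate ratio) ≈ (1/n)(1/μ₀ + k + 1/μ₁ + k), and power ≈ Φ(0.357/SE − 1.96), where 0.357 = |ln 0.70|.
- 12 months: μ₀ = 2, μ₁ = 1.4. Variance = (0.5 + 1 + 0.714 + 1)/110 = 0.0292, SE = 0.171, power = 0.55.
- 3 months: μ₀ = 0.5, μ₁ = 0.35. Variance = (2 + 1 + 2.857 + 1)/110 = 0.0623, SE = 0.250, power = 0.30.

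**4. Adding log(prior 12-month count + 0.5).** Gamma-Poisson simulation, negative binomial fit with robust standard errors, 4,000 runs per setting. Power without → with the prior count:

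| Stability | 3 months | 12 months | Variance ratio, 12 months |
|---|---|---|---|
| 50% | 0.301 → 0.315 | 0.55 → 0.57 | 0.95 |
| 60% | 0.306 → 0.327 | 0.56 → 0.60 | 0.92 |
| 70% | 0.300 → 0.326 | 0.55 → 0.61 | 0.89 |
| 85% | 0.296 → 0.338 | 0.56 → 0.67 | 0.76 |

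Check on the last row: 0.171 × √0.76 = 0.149, and Φ(0.357/0.149 − 1.96) = 0.67. With 99 per arm (10% loss), 12-month power is 0.51 → 0.53 at 50% stability and 0.51 → 0.63 at 85%.

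Sensitivity at 12 months, for 50% / 85% stability:
- 1 event a year: 0.430 → 0.446 / 0.442 → 0.491
- 4 events a year: 0.664 → 0.674 / 0.638 → 0.786
- dispersion 2: 0.397 → 0.381 / 0.380 → 0.486

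So there is no gain when dispersion is high and stability low. Type I error in the settings checked (60% and 100% stability, 3 and 12 months) was 0.045 to 0.058 unadjusted and 0.048 to 0.054 adjusted.

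**5. Adding the strata.** 220 children, blocks of 4 in six WeeFIM-by-age cells, 60% stability, 3,000 runs. Power with neither / strata / prior count / both:
- 12 months, risk unrelated to strata: 0.546 / 0.553 / 0.593 / 0.595
- 12 months, risk rising 1.5-fold per WeeFIM level: 0.568 / 0.611 / 0.618 / 0.644
- 12 months, risk doubling per level: 0.560 / 0.665 / 0.632 / 0.688
- 3 months, 1.5-fold per level: 0.304 / 0.319 / 0.325 / 0.330

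A second simulation used a different risk model, with strata explaining 5% of log-rate variance and 198 children analysed. Strata alone cut the standard error by 1 to 2%, and strata plus prior count by about 1 to 13%. At the top of that range, 220/0.871² ≈ 290, so 220 adjusted children carry the information of about 290 unadjusted ones.

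**6. Standard error when strata are ignored.** With no treatment effect and risk doubling per WeeFIM level, the unadjusted test rejects 3.1% of the time, against 5.2% with strata. A separate 500-run check gave 3.6%, with a typical reported SE of 0.163 against an actual SD of 0.143. The unadjusted test is then conservative.

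**The case against.** Item 9 asks for a summary, and one sentence on a secondary outcome may simply omit covariates that were always intended. The WeeFIM sentence in Data Collection points that way. This stands in part: the text is silent and does not declare an unadjusted analysis. But that sentence ties WeeFIM to no count model, the promise of similar models covers linear mixed models, and no section supplies a prior-use covariate.

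The operational sections describe about 3 months of app use and two follow-up surveys. The 12-month schedule appears only in the AIM 2 analysis text. If 3 months is right, the gain is small. This stands. The strata gains also depend on an assumed link between WeeFIM and risk; without one they are close to nil, though adding strata then costs nothing.

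Three stronger readings are tempting and not supported.

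- **That the unadjusted comparison is biased.** Randomisation protects it.
- **That the loss is large.** At 100% stability the simulated 12-month power rises from 0.55 to 0.76, but that requires every child's risk to be unchanged, and nothing in the documents suggests it.
- **That the zero-inflation option would produce a misleading ratio.** Structural zeros of 40% versus 55% with equal means of 3 would give a count-part ratio of 1.00 and an overall ratio of (0.45 × 3)/(0.60 × 3) = 0.75. But the plan says that the rate is compared, which points to the overall ratio. No section suggests that structural zeros differ by arm, and if they do not, the two ratios coincide. The trigger, read literally, is met in 53 to 59% of data sets with no zero-inflation, about what chance gives, and the plan makes the step optional. What remains is detail worth fixing in advance.

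**Conclusion.** The point holds as a minor one, for consideration. The count model names neither the strata used at randomisation nor a prior-use count, and the plan's own argument for adjusting CPCHILD applies here too. There is no bias. For the prior count alone, the assumed base case gives a gain of about 1 to 4 power points at 3 months and 2 to 11 points at 12 months, at 50 to 85% stability. Strata add to this only if risk differs by stratum; if it differs strongly, omitting them also makes the test conservative.

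Confidence in the direction is good. Confidence in the size is limited, because event rate, dispersion, effect, stability and the relation of risk to WeeFIM are all assumed, and the follow-up length is itself unsettled in the documents.

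**What to change.** Specify the ED/hospital analysis as a negative binomial log-link model with:

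- treatment;
- the WeeFIM and age strata as used at randomisation;
- the log-transformed pre-randomisation ED/hospital count from the data warehouse, with a stated look-back window;
- log time at risk as offset. The offset guards against bias from unequal follow-up and is not there for precision.

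Report the overall arm rate ratio from this model as the main result. Keep any zero-inflated fit as a sensitivity analysis. Define the count window from randomisation once the 3-month and 12-month follow-up passages are reconciled.

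**Cost.** The strata are free, since they are already collected. One point of wording is needed: the stated population is "Children age 1-20 years old with complex medical conditions and their parent caregivers", while the age strata stop at 18, so the stratum for 19- and 20-year-olds must be stated. The prior count costs one look-back field in the extract. The waiver's list of encounter and admission dates and the retrospective portion make it likely that the field can be obtained, but its reach before randomisation should be confirmed before the model is fixed. The rest is a few sentences of SAP text, best written before any arm-level counts are seen.
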